#### Potential exceptions to study procedures:

Participants already randomized to prazosin versus placebo prior to approval of the protocol modification instituting an initial, phase I open-label phase will continue to receive prazosin versus placebo in a double-blind fashion without alteration. Similarly, an individual who is participating in the study only via dual-enrollment (where the prazosin versus placebo is being administered as part of another study, and it is only assessments being conducted as a part of this study), will continue to be directly enrolled in the phase II version of the trial. All changes in study procedures will only apply to subjects who have not yet been randomized.

PTSD/TBI Glymphatic Protocol Version 3	VA Puget Sound IRB Protocol Template Version: 2/2015	Page 29 of 45
Revised 11/02/2018	,	

Phase I is designed to run until at least 22 participants have completed the full protocol, and their data has been analyzed. As discussed below in the data analysis section, if at the end of phase I the results are potentially consistent with a clinically significant effect, but do not yet meet statistical significance, we will continue the open label portion until we have 37 subjects who have completed the study (15 subjects beyond the initial 22), which is expected to involve 26 additional subjects screened when allowing for expected screen failure and dropout rates.

Some participants may also be (or have been in) in another study longitudinal study of mTBI that is being conducted by the MIRECC research group. If these participants have also agreed to have samples and data stored in the Behavioral Neurosciences Group (BNG) research repository (MIRB #00891, [name] PI), many screening/study assessments and the baseline sample collection may not need to be repeated (as described below).

The MIRECC research group is also conducting a study of the potential efficacy of prazosin in relieving post-traumatic headaches in Veterans with mTBI. Some of these participants will also be eligible for participation in this study. We wish to allow these participants to be in both studies simultaneously in order to maximize scientific learning and medical advances while minimizing participant burden. It also limits potential bias in the results of this study that might come if participants that qualified for competing local studies were enrolled at lower rates than their prevalence in the local community.

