#### 2. Baseline 1:

- a. Any previously completed WTAR may be substituted for the WTAR for the baseline 1 visit of this study.
- b. Any other component of the baseline 1 visit may be taken instead from an equivalent item previously carried out as long as it is completed within one month of the baseline LP. Although we will try to carry out these assessments in an order and configuration that is consistent across participants, this will not be an absolute requirement; for example, if

PTSD/TBI Glymphatic Protocol Version 3	VA Puget Sound IRB Protocol Template Version: 2/2015	Page 30 of 45
Revised 11/02/2018		

a participant has completed the WTAR two years ago and the ACT and SDMT one week ago, we will only include the CVLT, dot counting test, emotional Stroop test, and PVT for the baseline 1 neurocognitive testing, as the repeated-measure effects from repeating the ACT and SDMT so close together would be more of a concern than the variability in administration context.

- 3. Baseline 2: Any LP completed in the two weeks prior to scheduled randomization date and with sufficient CSF sample collected for our primary outcome measures will be allowed to substitute for the baseline LP. Any previous genetic testing from the prior 10 years may be substituted for equivalent genetic testing in this study.
- 4. Prazosin or placebo titration and maintenance: If a participant is concurrently enrolled in MIRECC prazosin vs. placebo study with overlapping inclusion/exclusion criteria the dosing schedule and data collected from stable dose study treatment period of the **other** study will be used (instead of the schedule for this study), if the following conditions are met:
  - a. The target dose per day of study drug is within 25% of the target dose per day in our study
  - b. The procedures performed at end of study visits 1 and 2, including the associated ambulatory monitoring, will be completed after the participant completes the study treatment period of the concurrent study. We will attempt to coordinate study schedules so there is a mid-point visit that matches when our Stable Dose week 4 visit would be scheduled.
- 5. End of study assessments: substitutions will be allowed as with the baseline assessments, described above.

Any non LP visit-related adverse events will be reported to the IRB for both studies, and it will be noted that the participant is in both studies simultaneously.

Schedule of Study Visitsa:

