Primary outcome measures will be CSF total-tau, p-tau181, and Aβ42. For each outcome, we will use a linear regression model to compare, between treatment groups, the within-subject changes in biomarkers from baseline. The model will include concentration at study completion as the response (dependent) variable, and the concentration at baseline and treatment group as the predictor (independent) variables, along with the covariates age, gender, APOE\*4 status, and blast exposure quantification. To account for dropouts and subjects who have their final biomarker assessment prior to 10 weeks, we will also use a linear mixed-effects regression model with biomarker concentration as the response variable, and the predictor variables time, treatment group, and a time by treatment group interaction term, along with the same covariates as for the linear regression model. Exploratory analyses will be conducted of the interaction among biomarkers; sleep and ambulatory monitoring variables; participant-reported symptoms of PTSD, depression, and postconcussive symptoms; and cognition.

Data will be analyzed by co-investigator [name], with consultation as necessary with the MIRECC biostatistician, [name], regarding the analysis plan and interpretation.

Data Management: All study information will be recorded on standardized CRFs. Forms will be labeled with study code numbers only. Code numbers will be assigned sequentially, and will not include participant initials or any other personally identifiable information. Source documents, which may include identifying information, will be maintained in locked files within a locked office. The study coordinators at VA Puget Sound and Madigan will keep the key between the identity of participants and study code number. The key will not be shared with to anyone other than members of the research team.

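### Dual-enrolled participants enter phase II on another study's treatment and schedule, the models have no term for source, and the text on when their final LP is taken must be reconciled

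*Combined protocol and SAP*

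**What the plan says.** All references are to the combined protocol and SAP.

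- **Treatment source.** Section 5.4 (Potential exceptions to study procedures) describes participants for whom "the prazosin versus placebo is being administered as part of another study", with this study contributing only the assessments. They "will continue to be directly enrolled in the phase II version of the trial".
- **Schedule.** Under item 4 of the same section, the dosing schedule and stable-dose data of the other "study will be used (instead of the schedule for this study), if the following conditions are met". Condition (a) is: "The target dose per day of study drug is within 25% of the target dose per day in our study". Condition (b) places the procedures of end-of-study visits 1 and 2, which include the final LP, after the other study's treatment period. Neither condition sets a minimum time at steady dose.
- **Substitution.** Item 3 accepts "Any LP completed in the two weeks prior to scheduled randomization date" as the baseline LP. Item 5 says of end-of-study assessments that "substitutions will be allowed as with the baseline assessments, described above".
- **This trial's allocation.** Section 5.5 specifies 2:1 randomisation, stratified by gender and by TBI/PTSD group.
- **Models.** The Section 5.5 regression takes "the concentration at baseline and treatment group as the predictor (independent) variables", plus age, gender, APOE*4 status and blast exposure. A mixed model with time, treatment and their interaction uses the same covariates and is added for dropouts and for final samples taken before 10 weeks. Neither model identifies where a participant was randomised, and no analysis separates dual-enrolled participants.

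**The concern.** Randomisation protects a treatment comparison within the list that generated it. Dual-enrolled participants receive their drug in a separate prazosin versus placebo study, so this trial's 2:1 list very probably does not govern them. If two lists with different ratios are pooled without a source term, the arms contain different proportions from each source, and any difference between sources in CSF change is partly credited to prazosin or to placebo.

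A difference between sources is plausible. The concurrent study named in Section 5.4 concerns post-traumatic headache in Veterans with mTBI, whereas this trial also admits Veterans with PTSD and no TBI (Section 5.3). The dosing schedule may differ as well, and TBI/PTSD group is not a covariate.

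The second issue is when the primary outcome is measured. Aim 1 tests titration plus 5 weeks at steady dose. For dual-enrolled participants the text does not secure that exposure, nor does it say clearly when the final LP falls relative to it.

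**Working it through.** **Inputs from Section 5.5.** Baseline mean 294 ng/L, SD 54 ng/L, within-person correlation 0.98, 60 completers split 40:20, target decrease about 5%.

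**The plan's own figures.** SD of change = 54 × √(2 × (1 − 0.98)) = 54 × 0.2 = 10.8 ng/L, as stated. The target is 0.05 × 294 = 14.7 ng/L.

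**Inputs not in the documents, assumed here.** The number of dual-enrolled completers (6, 12 or 18 of 60), the other study's ratio (1:1), and the difference between sources in mean CSF change, g, left after covariate adjustment (10.8 ng/L, one SD of change, or 2.7 ng/L, a quarter of that). The treatment effect is taken to be the same in both sources.

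**Formula.** Bias of the pooled treatment difference ≈ (dual-enrolled share on prazosin − dual-enrolled share on placebo) × g.

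**Central case, 12 dual-enrolled.** Direct: 48 at 2:1 = 32/16. Dual: 12 at 1:1 = 6/6. Shares: 6/38 = 0.158 and 6/22 = 0.273. Difference: −0.115.

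| Dual-enrolled | Difference in share | Absolute bias, g = 10.8 | Absolute bias, g = 2.7 |
|---|---|---|---|
| 6 | 3/39 − 3/21 = −0.066 | 0.71 ng/L (5% of 14.7) | 0.18 ng/L (1%) |
| 12 | 6/38 − 6/22 = −0.115 | 1.24 ng/L (8%) | 0.31 ng/L (2%) |
| 18 | 9/37 − 9/23 = −0.148 | 1.60 ng/L (11%) | 0.40 ng/L (3%) |

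The direction depends on the sign of g. If the other study also allocates 2:1, 12 participants split 8/4, and 8/40 − 4/20 = 0, so there is no bias in expectation.

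**Precision cost of a source term, central case.** Pooled SE = 10.8 × √(1/38 + 1/22) = 2.89 ng/L. Stratified by source, the information is 1/(1/32 + 1/16) + 1/(1/6 + 1/6) = 10.67 + 3 = 13.67, so SE = 10.8/√13.67 = 2.92 ng/L. The loss is about 1%.

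**Timing: the provisions side by side.**

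1. Aim 1 (Section 3.0) and Study Treatment Period (Section 5.4): titration, then at least 5 weeks at the achieved dose, then the final LP.
2. Item 4: the other study's schedule applies instead. The exposure condition concerns the daily target dose, not duration, and the other study's length is not given. Section 5.6 breaks the blind at the end of whichever study is longer, so unequal lengths are foreseen.
3. Item 4b: the final procedures follow the other study's treatment period.
4. Potential exceptions to visit schedule (Section 5.4): end-of-study measures are barred after prazosin has been stopped. Items 3 and 4 are compatible only if drug continues until the LP, and the text does not say that it does when another study supplies it. The same sentence also dates the end-of-study limit from the baseline LP, which cannot fit an outcome taken after titration and 5 weeks.
5. Item 5: the baseline substitution rules carry over, but the baseline LP window is tied to randomisation and no end-of-study window or anchor is defined.

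**The case against.** Every input that drives the bias is unknown: how many participants are dual-enrolled, the other study's ratio, and any source difference that remains after adjustment. A gap of one full SD is severe, being 73% of the target effect (10.8/14.7). Even then the central bias is about 0.4 of a standard error (1.24/2.89), and in a pilot the dual-enrolled group may be very small. All of this stands. It limits the size of the point but does not remove it, since the term costs almost nothing and protects the comparison whatever the ratio proves to be.

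The mixed model already anticipates final samples before 10 weeks. That is partial mitigation: it has no source term, does not address a sample taken after drug has stopped, and leaves the regression unchanged.

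A reader might infer that item 5 plainly permits the final LP before 5 weeks of steady dosing, for instance at 5 − 2 = 3 weeks. The documents do not support that. Item 4b places the LP visit after the other study's treatment period. In the schedule of study visits, the LP substitution footnote is attached to baseline part 2 only. The two-week window is tied to randomisation and has no end-of-study counterpart, and item 5 can be read as covering clinical and cognitive tests alone. Item 4b also calls a visit matching stable-dose week 4 a mid-point, which suggests a treatment period longer than 5 weeks. An early LP is one possible reading of item 5. A late or off-drug LP is equally open.

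**Conclusion.** The point holds as a cheap improvement to the analysis plus an inconsistency in the text. Participants treated under another study enter phase II, and neither specified model distinguishes them. That the other study also allocates them, and that they are pooled, is a fair inference rather than an explicit statement.

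Under the assumed 1:1 ratio, the bias runs from 0.2 to 1.6 ng/L over the range shown, with 1.2 ng/L in the central case at a one-SD gap. It is zero if the other study also allocates 2:1. A reader should not conclude that the phase II comparison is biased: the documents give neither the ratio nor the number of dual-enrolled participants, so the actual size cannot be computed.

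On timing, the firm finding is that no minimum steady-dose duration is a condition of dual enrolment, and that items 4b and 5 and the bar on measures after stopping do not together fix when the final LP is taken.

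**What to change.** 1. In Section 5.5, add randomisation source (this trial or the concurrent study) as a fixed effect in both the primary regression and the mixed model.
2. Specify one sensitivity analysis that excludes dual-enrolled participants.
3. Reconcile items 4, 4b and 5 of Potential exceptions to study procedures, and the limit on end-of-study measures in Potential exceptions to visit schedule, with Aim 1 and the Study Treatment Period. State whether item 5 covers the LP and, if it does, what window and anchor date apply. How the timing is settled is for the sponsor and investigators to decide.

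The cost is one degree of freedom (SE about 2.92 instead of 2.89 ng/L in the central example), one extra model run and a short clarification of the text. The changes should be made before unblinded phase II data are analysed.

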#### 5.3 Inclusion/Exclusion Criteria

#### Inclusion criteria:

- Age ≥ 21 years
- Veteran of the U.S. Armed Forces
- Ability to complete psychometric and other clinical assessments in English
- No clinically significant laboratory abnormalities at screen
- Platelet count >100,000/mm2 within two weeks of lumbar puncture (LP)
- Body mass index (BMI) between 18 and 36 inclusive (BMIs outside this range may make LPs for CSF collection difficult to perform). If a potential participant has a BMI over 36 but still in the 30s, they may be included if the clinician determines an LP would not be difficult to perform.
- Women of childbearing potential must agree to abstain from sexual relations that could result in pregnancy or use an effective method of birth control acceptable to both participant and the study clinician during the study. Men are not required to use contraception during the study
- Meeting criteria for at least one of the following:
  - 1. History of mild or moderate TBI:
    - Exposure to at least one blast or experiencing at least one collision of the head associated with acute symptoms that meet VA/DoD criteria for mild or moderate TBI (loss of consciousness, if present, <24 hours; posttraumatic amnesia, if present, <1 week; Glasgow Coma Scale (if available) 9-15)

    - o >6 months since last TBI.
  - 2. Documented diagnosis of PTSD related to combat trauma (from any conflict)

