panel, vitamin B12, thyroid function, and coagulation (PT and PTT/INR) tests and a routine urinalysis will be performed. Female participants of childbearing potential will have a urine pregnancy test, which must be negative in order to continue study participation. If it is found that a potential participant does not meet the inclusion criteria, follow-up care will be coordinated.

Participants who remain eligible after screening will be asked to undergo the following study procedures:

At-home BP monitoring and monitoring of sleep activity (description of equipment and sleep logs below after the description of study visits): At the end of the screen visit, we will place the at-home BP monitoring equipment on the study participant. The participant will remove the BP monitoring equipment after 24 hours and will bring it back at Baseline visit 1. We will also give the study participant an Actiwatch to wear until Baseline visit 2 (typically 9-14 days total, although possible alterations in this timing are discussed under "Potential exceptions to visit schedule" below). Instructions for wearing the Actiwatch and filling out a sleep diary during this time will also be given to participants.

Baseline visit 1—Clinical and Cognitive Assessments, pupillometry, placement of HR monitor: Health history and list of medications will be updated as needed. Vital signs will be taken. Behavioral, functional, and cognitive instruments/questionnaires will be administered as outlined in the schedule of study visits. If it has been longer than 2 weeks since screen (or if BL visit 2 is expected to be longer than two weeks from screen), about 5-10 ml of blood will be collected for blood count and coagulation tests.

Participants will return the BP monitoring equipment and will have an ambulatory HR monitor placed. When possible, the HR monitor will be placed at a point in the visit prior to the completion of the neurocognitive testing, in order to allow the degree of correlation between the results of the heart rate variability analysis and the pupillometry analysis to be assessed; this will then count as the beginning of 24 hours of use, after which the participant may remove the HR monitor. Participants will continue wearing the Actiwatch and filling out sleep diaries until the baseline 2 visit.

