In this case, once the potential participant is recruited and enrolled into the related headache study and the BNG repository, and if the potential participant and both study PIs agree, we will alter the schedule of this study as described below and will place information gathered in each study in the BNG repository in real time so that it will be possible to share information between studies so that participants may be able to be in both studies at the same time without having to repeat study evaluations and other procedures.

- 1. Screen: All items except study consent and vital signs that are scheduled for the screening visit may be taken instead from the same item previously carried out within the prior year with the following exceptions:
  - a. a previously completed TLEQ will only be used if it contains the modifications that include collection of information on the timing of events;
  - b. updates will be obtained for medical and psychiatric history and current medications;
  - c. physical and neurological exams will be repeated if they were last done more than 3 months ago, or 4 weeks ago if there are any elements in the medical or psychiatric history, vital sign data, or on previous physical/neurologic exam that suggest the Veteran may have increased risk for adverse outcomes with prazosin;
  - d. a general screening question will be asked to ascertain whether there may have been any potentially traumatic experiences since the SCID, CAPS, and TLEQ were last completed, and if so, they will be redone as indicated.

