#### **Detailed Descriptions of Study Assessments:**

• Structured Clinical Interview for DSM-5 Axis I Disorders (SCID5): A widely used structured interview that assesses Axis I psychiatric history. The SCID has very good reliability and validity. The SCID will be used at the screen visit to rule out exclusionary diagnoses and to describe the subject sample.

PTSD/TBI Glymphatic Protocol Version 3	VA Puget Sound IRB Protocol Template Version: 2/2015	Page 32 of 45
Revised 11/02/2018		

b If more than two weeks will have passed between screen LP visit, then platelet count and clotting time labs will be drawn at these visits.

<sup>c If DNA is already available in a research repository, it will not be collected. If an LP has been performed within two weeks of randomization, and sample is available in the repository, LP will not be done at baseline visit 2.

<sup>dFor second and third QCC, an abbreviated follow up version will be used

<sup>e There may be up to three additional titration visits, which would add three weeks to the total length of the study.

f Blood and saliva for DNA will only be collected at first biomarker collection visit.

g At routine titration / follow up visits, an abbreviated, 1 page version of the PSQI will be used.

- Structured Clinical Interview for DSM-IV Axis I Disorders (SCID-IV): Previously version of the same widely used structured interview that assesses Axis I psychiatric history. The SCID has very good reliability and validity. The SCID will be used at the screen visit to rule out exclusionary diagnoses and to describe the subject sample. If clinically or logistically more accessible, due to previous assessments undergone by this particular subject or new information on the relative utility of the different instruments, we may carry out and/or accept the SCID for DSM-IV or the MINI in place of the SCID5. The SCID for DSM-IV has been a widely used structured interview that assesses Axis I psychiatric history according to the DSM-IV criteria, and is still administered in many of the ongoing research studies here at the MIRECC. The Mini International Neuropsychiatric Interview (MINI)(Sheehan et al., 1998) is a widely used alternative that is also designed to take into account the International Classification of Disease (ICD) 10 criteria, and is widely used internationally.

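### Participants shared with related studies may reuse year-old screening labs, and the two-week pre-LP redraw counts from 'screen' and not from the blood draw, so an outdated PT/PTT/INR can stand at the baseline LP

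*Combined protocol and SAP*

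**What the plan says.** All of this is in the combined protocol and SAP.

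- **Screening labs.** Section 5.4, Screening Procedures, lists a blood count, a chemistry panel, vitamin B12, thyroid function "and coagulation (PT and PTT/INR) tests".
- **Redraw before the LP.** Under Baseline visit 1, blood for a count and clotting tests is taken "If it has been longer than 2 weeks since screen", or if Baseline visit 2 is expected to fall beyond that interval. Footnote b to the Schedule of Study Visits gives the same rule: "If more than two weeks will have passed between screen LP visit, then platelet count and clotting time labs will be drawn".
- **Usual interval.** At the end of the screening visit the participant receives an Actiwatch "to wear until Baseline visit 2 (typically 9-14 days total").
- **Reuse.** Under Potential exceptions to study procedures, item 1, everything except consent and vital signs "scheduled for the screening visit may be taken instead from the same item previously carried out within the prior year". Exceptions a to d concern the TLEQ, updates of history and medications, the exams, and a question about new trauma. Labs are not named. For the exams, exception c sets a shorter limit: "physical and neurological exams will be repeated if they were last done more than 3 months ago".
- **Baseline 1 substitution.** Item 2b says that components of that visit other than the WTAR "may be taken instead from an equivalent item previously carried out as long as it is completed within one month of the baseline LP".
- **Limits that do not depend on 'screen'.** The inclusion criteria in section 5.3 ask for "Platelet count >100,000/mm2 within two weeks of lumbar puncture (LP"), and Baseline Visit 2 includes a platelet test on the day. Clotting abnormalities are listed in section 5.3 as a contraindication to LP, but no date is set for the test.

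**The concern.** Each rule is reasonable alone. In the ordinary course, blood is drawn at the screening visit, so counting from screen and counting from the draw give the same answer. Reuse separates the two dates: the blood may have been drawn months before, while the two-week clock starts at a screening visit where no blood was taken.

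The clotting check is there to find a current abnormality before the study's main invasive procedure. An old result may no longer describe the participant. The update of history and medications would reveal a new anticoagulant, but not a clotting change without symptoms. What is at stake is participant safety at the baseline LP. Sample size, randomization and the planned analyses are not touched.

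**Working it through.** The plan states no maximum age for the clotting result, so there is no figure to reproduce. The check is date arithmetic on the plan's own windows.

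**Inputs**
- Reuse window: one year, taken as 365 days counted back from this study's screening visit (an assumption; the text does not give the anchor).
- Longest interval from screen to LP that does not trigger a redraw: 14 days (Baseline visit 1; footnote b).
- Typical interval from screen to Baseline visit 2: 9-14 days.
- Baseline 1 substitution window: one month, taken as about 30 days (item 2b).
- The plan's standard for these labs: two weeks, or 14 days.

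**Reading A: 'screen' is this study's screening visit**
- Age at LP = age of the reused lab at screening + interval from screen to LP.
- Maximum = 365 + 14 = 379 days; 379 / 7 = 54.1 weeks.
- Over the standard by 379 - 14 = 365 days; 379 / 14 = 27.1 times the standard.
- For a year-old lab at the typical interval: 365 + 9 = 374 to 365 + 14 = 379 days, with no redraw triggered.
- If the prior year were counted back from the LP itself, the maximum would be 365 days.
- The standard can be exceeded without an extreme case. At a 9-day interval, any lab drawn more than 14 - 9 = 5 days before screening is past two weeks at the LP. At 14 days, any lab drawn before screening is (14 - 14 = 0).

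**Reading B: 'screen' is the date of the reused labs**
- A lab more than 14 days old at the LP triggers a redraw at Baseline 1, and the two-week standard is kept.
- If item 2b were applied to that redraw, a result of up to about 30 days could stand: 30 - 14 = 16 days over, or 30 / 14 = 2.1 times the standard.

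**Search for another rule that dates the clotting result**
- The two-week inclusion criterion and the LP-day test cover platelets only.
- The exclusion for clotting abnormalities has no test window.
- Footnote a to the schedule allows reuse of procedures done in another study, but it gives no period.
- At the end-of-study LP, more than two weeks have passed since screen on either reading, and the schedule marks the screening labs there under footnote b. The narrative for those visits says blood will not be collected; I follow the schedule.

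**The case against.** The strongest reply is that footnote b has only one purpose, to limit the age of these labs. On that purpose 'screen' should mean the day the screening blood was drawn, and a year-old result would always be redrawn. This is a fair reading, and under it the standard holds. But neither statement of the rule says so, and a coordinator who counts from the visit would be following the text.

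A reader might also infer that even the favourable reading breaks the limit, because item 2b allows a month. The documents do not establish that. Item 2b is a general permission whose worked example concerns neurocognitive tests, and footnote b is the specific rule for these labs. The 30-day figure arises only if the general rule is allowed to override the specific one.

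Further points stand in part:
- Platelets and clotting are normally one draw, and every participant needs a platelet count within two weeks of the LP. In practice that draw would often refresh PT/PTT/INR too. The LP-day platelet test could meet the criterion alone, however, so the pairing is not guaranteed.
- The path needs enrolment in the headache study and the repository, agreement of the participant and both principal investigators, and a baseline LP that is not itself substituted under item 3. The number of such participants is not given.
- Health and medications are reviewed again on the LP day, and anticoagulant use is an exclusion. What remains is a symptomless clotting change since the reused result. The documents give no rate for that.
- The shorter exam limits are a weak guide to acceptable lab age. The 4-week limit is tied to prazosin risk, not to bleeding at LP.

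**Conclusion.** The concern holds as a gap in the wording with a safety consequence. On the shared-study path, the text permits a PT/PTT/INR result well beyond the plan's own two weeks at a baseline LP done in this study. The size depends on what 'screen' means: at most about 379 days if it is the visit, and no breach if it is the lab date and item 2b is kept away from labs. The 379 days is a permitted maximum, not an expected value, and it rests on counting the prior year back from screening.

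Three wider conclusions might be inferred, and the documents do not support them:
- **Platelets are also exposed.** They are not, given the two-week criterion and the LP-day test.
- **Chemistry needs its own limit, such as three months.** The plan sets no redraw interval for chemistry for any participant, so there is no internal standard that reuse contradicts.
- **The pregnancy test has the same gap.** The safety text in section 5.0 requires a negative test within one week of the first dose, whatever the start date, and a negative test before any LP.

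**What to change.** 1. Under Potential exceptions to study procedures, item 1, add exception e: *Platelet count and PT/PTT/INR must be drawn within two weeks before the LP.*
2. In Baseline visit 1 and footnote b, count the two weeks from the draw date of the last platelet and clotting labs.
3. State in item 2b that the one-month substitution does not apply to these labs. Item 5 carries the baseline substitutions over to the end of study, so one sentence can cover both.

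With these changes the oldest permitted clotting result at the baseline LP falls from 379 days to 14 on the literal reading, and the two readings agree. The cost is one 5-10 ml draw, the volume the plan already gives, at the scheduled Baseline 1 visit for participants whose clotting labs would otherwise be too old. No visit is added, and sample size and analysis are unchanged.
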